11.3 Determination of Sample Size and Statistical Rationale

The sample size for this study is based on recently obtained 12-month results of the OPH2003 pivotal international, multicenter, randomized, double masked, sham-controlled clinical trial that was performed to evaluate the safety and efficacy of Zimura in patients with geographic atrophy secondary to AMD. The prespecified primary endpoint, mean change in GA growth over 12 months, equivalent to the mean rate of GA growth used in this study, was measured by fundus autofluorescence (FAF) based on readings at three time points (Baseline, Month 6, and Month 12) and was calculated using the square root transformation of the GA area. The FAF images were assessed by an independent masked reading center. The reduction in the mean rate of GA growth over 12 months was 0.11 mm ($p = 0.0072$) for the Zimura 2 mg group compared to the Sham control group.

In this Phase 3 trial, the primary analyses will be based on the comparison of the estimated reduction in the mean rate of GA growth over 12 months for Zimura 2 mg group versus the Sham control group. By pre-specification, this study will obtain evidence regarding the effect of Zimura on the mean rate of growth (slope) estimated based on GA area measured by fundus autofluorescence (FAF) in at least 3 time points over 12 months, when compared with Sham (square root transformation). The FAF images will be assessed by an independent masked reading center. The effect of treatment on the square root transformation of the GA area will be assessed using a mixed model for repeated measures model (MMRM) including stratification factors.

A total of approximately 400 patients will be randomized. If the 2 mg dose of Zimura truly provides a 0.11 mm reduction in the mean rate of GA growth over 12 months, then the trial will have 97% power to detect that effect at the two-sided significance level of 0.05. **Statistical**

significance at the two-sided significance level of 0.05 will be achieved for an estimated 0.057 mm reduction in the mean rate of GA growth over 12 months.

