11.5 Randomization Procedure

Patients will be centrally allocated to one of the two treatment groups by a dynamic minimization procedure using clinical site in a 1:1 ratio stratified by factors known to be of prognostic importance in AMD:

- Baseline visual acuity < 50 ETDRS letters (20/100 Snellen equivalent) vs \geq 50 ETDRS letters
- Size of Baseline geographic atrophy (< 4 disc areas vs \geq 4 disc areas)
- Pattern of Fundus Auto Fluorescence (FAF) at the junctional zone of GA (None/focal vs banded/diffuse)

Patients initially randomized to Zimura 2 mg at Day 1 will be re-randomized at Month 12 in 1:1 ratio to Zimura 2 mg monthly vs every other month (please see 11.1 Study Design) using the same minimization procedure as for the initial randomization (i.e. using the same factors at Baseline).

Randomization will be performed using an IRT system based on the stratification information above to randomize each subject and assign a treatment arm.

The IRT system will be used to assign masked study kits to patients throughout the duration of the trial. All study medication must be dispensed using the IRT system. At each dispensing visit the IRT system will allocate each study drug kit(s) using the kit number on the label of the study medication kit.

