The sample size for this study is based on the 12-month results of the OPH2003 (GATHER1) pivotal international, multicenter, randomized, double masked, sham-controlled clinical trial that was performed to evaluate the safety and efficacy of Zimura in patients with geographic atrophy secondary to AMD. The prespecified primary endpoint, mean change in GA growth over 12 months, equivalent to the mean rate of GA growth used in this study, was measured by fundus autofluorescence (FAF) based on readings at three time points (Baseline, Month 6, and Month 12) and was calculated using the square root transformation of the GA area. The FAF images were assessed by an independent masked reading center. The reduction in the mean rate of GA growth over 12 months was 0.11 mm ($p = 0.0072$) for the Zimura 2 mg group compared to the Sham control group.

A total of approximately 400 patients will be randomized in the GATHER2 trial. The effect of treatment will be assessed on the square root transformation of the mean rate of GA growth (slope) estimated based on GA area measured in at least 3 time points over 12 months, where the analysis of variance will include the stratification factors. Suppose the standard deviation for the primary endpoint in GATHER2 is as assumed in the design of the GATHER1 trial, (which is 7% higher than was actually observed in that trial.) If the 2 mg dose of Zimura truly provides a 0.11 mm reduction in the mean rate of GA growth over 12 months, then the trial will have 97% power to detect that effect when using a test statistic having (one-sided) 2.5% false positive error rate. Furthermore, the trial will have nearly 90% power to achieving an even more robust significance level at two-sided $p < 0.01$. Statistical significance at the traditional level of two-sided $p = 0.05$ would be achieved with an estimated 0.057 reduction in the mean rate of GA growth over 12 months. Note that the power of the trial will be slightly lower when using an alpha-level that would be adjusted by (two-sided) 0.001 for each DSMB meeting at which any data are reviewed.

RANDOMIZATION

Patients will be centrally allocated to one of the two treatment groups by a dynamic minimization procedure using clinical site in a 1:1 ratio stratified by factors known to be of prognostic importance in AMD:

[figure not shown]

CONFIDENTIAL

- Baseline visual acuity < 50 ETDRS letters (20/100 Snellen equivalent) vs. \geq 50 ETDRS letters

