The primary analysis will use the ITT population and will be based on a Mixed Model for Repeated Measures (MMRM) to compare the treatment groups. This analysis provides valid estimates as long as the missing data mechanism fulfills the Missing at Random (MAR) assumption. However, sensitivity analyses (see Section 7.4.1) will be performed to assess the potential magnitude and direction of the impact of missing data.

CONTROL OF ALPHA

The overall (one-sided) false positive error rate in this trial is 0.025.

An alpha-level adjustment will be made in the assessment of statistical significance at the time of the final analysis, equal to (two-sided) 0.001 for each DSMB meeting for any look at the data. There will not be formal interim analyses for early termination for benefit and, in turn, the DSMB will not make recommendations for early termination even if emerging data would provide strongly favorable evidence for benefit. Rather, the principal justification for the DSMB to have access to emerging data on efficacy as well as safety data during DSMB meetings is to enable the DSMB to more effectively safeguard interests of study participants through a properly informed assessment of benefit-to-risk.

ANALYSIS OF PRIMARY EFFICACY OUTCOME

The primary efficacy endpoint is the mean rate of growth (slope) estimated based on GA area measured by FAF in at least 3 time points: Baseline, Month 6, and Month 12 (square root transformation). To eliminate the dependency of GA growth rates on the Baseline lesion size (Feuer et al., 2013), instead of using the observed GA area measurement, the square root of the GA area will be used in the analysis.

Primary Estimand

In alignment with the primary objective of the study, the main estimand to be used for the evaluation of the primary outcome is described as:

The difference in the mean rate of growth (slope) estimated based on GA area measured by FAF in at least 3 time points: Baseline, Month 6, and Month 12 (square root transformation) between treatment conditions (Zimura versus Sham) in the target patient population, regardless of any non-adherence to or interruption of study treatment, and regardless of initiation of alternative treatment.

The following 5 attributes define the main estimand for primary endpoint evaluation:

A. Population:

CONFIDENTIAL

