A mixed model for repeated measures (MMRM) will be applied to all available data, using as response variable the square root of GA area measured by FAF in at least 3 time points: Baseline, Month 6, and Month 12. The MMRM will be used to assess the difference between the treatment groups in terms of the rate of growth of the square root of GA area (slope) over 12 months. Previous trial OPH2003 (GATHER1) showed the change in the square root of geographic atrophy to be remarkably linear over time. As a result, a linear model is not only convenient and easily interpretable, but it is also appropriate given the natural history of the disease. A model will be fitted by using restricted maximum likelihood (REML) and include Baseline VA (< 50 letters vs. ≥ 50 letters), and pattern of FAF at the junctional zone of GA (none/focal vs. banded/diffuse) as used in the randomization as covariates. For the model, fixed effects will include time, treatment, Baseline VA (< 50 letters vs. ≥ 50 letters), pattern of FAF at the junctional zone of GA (none/focal vs. banded/diffuse), treatment by time interaction, Baseline VA (< 50 letters vs. ≥ 50 letters) by time interaction, and pattern of FAF at the junctional zone of GA (none/focal vs. banded/diffuse) by time interaction. The model will include an unstructured modelling of within-subject correlations. If this analysis fails to converge, alternative structures (e.g., heterogeneous autoregressive, heterogeneous compound symmetry, autoregressive, or compound symmetry, in this order) will be considered. The Kenward-Roger approximation will be used to estimate denominator degrees of freedom. The test of difference between the two arms in the mean rate of growth

CONFIDENTIAL

(slope) of the square root of GA area over 12 months will be assessed by testing the appropriate contrast of the model parameter estimates.

[Redacted content]

CONFIDENTIAL

[Redacted text block]

[Redacted text line]

[Redacted text line]

[Redacted text line]

[Redacted text line]

[Redacted text line]

[Redacted text line]

[Redacted text line]

[Redacted text line]

[Redacted text line]

[Redacted text line]

[Redacted text line]

[Redacted text line]

[Redacted text line]

[Redacted text line]

[Redacted text line]

[Redacted text line]

[Redacted text line]

[Redacted text line]

[Redacted text line]

[Redacted text line]

CONFIDENTIAL

- █ [REDACTED]
- █ [REDACTED]
- █ [REDACTED]
- █ [REDACTED]
- █ [REDACTED]
- █ [REDACTED]
- █ [REDACTED]

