Since November 16th, patients have been stratified correctly as indicated in the protocol based on their baseline geographic atrophy size: < 4 disc areas (10 mm²) vs ≥ 4 disc areas (10 mm²). The minimization procedure was not modified after November 16, 2020, because implementing any changes to this procedure would have meant putting the trial on hold while the changes were being implemented and validated. Furthermore, an inspection by the randomization center of the balance with respect to baseline geographic atrophy size achieved on November 16, 2021 provided reassurance that the minimization algorithm could continue unchanged.

CONFIDENTIAL

Sensitivity Analysis for Observed GA Measurement

The sensitivity of the results from the analyses of observed (non-square root transformed) area of GA over 12 months will be conducted using the same analysis model as specified in section 7.2.

[REDACTED]

[REDACTED]

[REDACTED]

[REDACTED]

[REDACTED]

- [REDACTED]

- [REDACTED]

- [REDACTED]

- [REDACTED]

[REDACTED]

Descriptive Summaries by Visit

The change in score from Baseline will be analyzed as continuous variables. The composite score and the scores of each sub-scales at Baseline and the changes from Baseline will be summarized descriptively by visit and by treatment group using the observed cases (missing values will not be imputed).

[REDACTED]

SUBSET ANALYSES

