4.2.1.2. Statistical Method

With a re-randomization at the end of Year 1, the initial stratification factors from the randomization are no longer applicable in the analysis of Year 2. Therefore, the stratifications factors will be removed from the MMRM model as in the primary analysis.

The revised model is described below.

A mixed model for repeated measures (MMRM) will be applied to all available data, using response variable of the GA growth area over time up to Month 24 in 5 time points: Baseline, Month 6, Month 12, Month 18, and Month 24. The MMRM will be used to assess the difference between the treatment groups in terms of the rate of growth (slope) of the GA over time of 24 months. Time is defined as a continuous variable in number of study days since the baseline assessment. Treatment groups include ACP EM, ACP EOM, and Sham. A model will be fitted

by using restricted maximum likelihood (REML) and include time, treatment, and treatment by time interaction as fixed effects, subject as random effect.

Notice that in the primary analysis at Year 1 (Month 12), the square root transformation of GA growth area was used. However, the mean GA growth (slope) has shown similar results with or without square root transformation. In addition, it is difficult to interpret the transformed data in context. Therefore, in the Year 2 analysis, the untransformed GA growth using observed GA area of measurement will be used as the primary endpoint.

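### The Year 1 primary MMRM omits baseline GA size, although the protocol says the model includes the stratification factors, and the raw-area sensitivity analysis reuses that model on a scale where growth depends on size

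*SAP*

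**What the plan says.** Protocol 11.5 describes allocation by a "dynamic minimization procedure using clinical site in a 1:1 ratio stratified by factors known to be of prognostic importance in AMD". It then lists three factors: baseline VA, "Size of Baseline geographic atrophy" (below versus at least 4 disc areas) and FAF pattern at the junctional zone. The Year 1 SAP repeats the list under Randomization.

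Protocol 11.3 says that the treatment effect on square-root GA area will be assessed with a "mixed model for repeated measures model (MMRM) including stratification factors". The sample-size text of the Year 1 SAP describes its analysis as one "where the analysis of variance will include the stratification factors". Neither statement names an exception.

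The operative model is under Analysis of Primary Efficacy Outcome in the Year 1 SAP (its section 7.2). There the "fixed effects will include time, treatment, Baseline VA" group and FAF pattern, plus treatment by time, VA by time and pattern by time. The sentence is complete and not redacted. GA size appears neither as a main effect nor with time.

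The same section gives the reason for the square root: "To eliminate the dependency of GA growth rates on the Baseline lesion size". The Sensitivity Analysis for Observed GA Measurement, on untransformed area, "will be conducted using the same analysis model as specified in section 7.2".

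GA size enters the Year 1 analyses in two other places: two sensitivity analyses for the stratification error, with 3-level size covariates, and the descriptive subgroups.

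**The concern.** A factor used in the allocation is normally carried into the analysis, and here the protocol commits to that without exception. A reader who follows protocol 11.3 and one who follows SAP section 7.2 would fit different primary models. No readable text records the omission as a change or explains it.

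The gap has more substance in the raw-area analysis. By the SAP's own account, growth in mm² depends on how large the lesion is at baseline, yet the model for that analysis has no size-by-time term. Size-related spread in growth then stays in the residual variation, and any chance difference in size between the arms passes into the estimated slope difference. At stake are some precision, protection against chance imbalance, and agreement between protocol and SAP on the primary model.

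**Working it through.** **1. The plan's own power figure.** Inputs from protocol 11.3: about 400 patients 1:1 (200 per arm), effect 0.11 mm, two-sided alpha 0.05, significance reached at 0.057 mm, power 97%. No SD is printed, so it is back-calculated:

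- SD = 0.057 / 1.96 × √(200/2) = 0.291 mm
- SE = 0.291 × √(2/200) = 0.0291 mm
- Power = Φ(0.11/0.0291 − 1.96) = Φ(1.82) = 96.6%

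The 97% reproduces. Because the SD comes from the 0.057 mm, this shows that the stated figures agree with one another. It does not check the SD independently.

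**2. Square-root scale.** If size explains a share R² of the slope variance, adjusting multiplies the SD by √(1 − R²). The documents give no R², so a range is assumed.

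| Assumed R² | SD (mm) | Power | Smallest significant estimate (mm) |
|---|---|---|---|
| 0 | 0.291 | 96.6% | 0.0570 |
| 0.02 | 0.288 | 96.9% | 0.0564 |
| 0.05 | 0.283 | 97.3% | 0.0556 |
| 0.10 | 0.276 | 97.9% | 0.0541 |

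If the square root does what the SAP says, R² is near 0 and nothing is lost. If it does not, adjustment helps slightly.

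**3. How raw growth depends on size.** Protocol 4.3.4 gives a 27.38% reduction for 2 mg in the earlier trial. With 0.11 mm this implies Sham growth of 0.11/0.2738 = 0.402 mm/year. Growth in area from baseline area A is (√A + 0.402)² − A:

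- A = 4 mm²: 1.77 mm²/year
- A = 10 mm²: 2.70 mm²/year, which is 53% more (2.70/1.77)

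**4. Precision on the raw scale.** Assumptions: baseline root-area mean 2.5 to 2.8 mm and SD 0.5 to 0.9 mm (not in the documents); root-scale growth with mean 0.402 and SD 0.27 mm; reading error 0.075 mm per visit. The implied SD of 12-month change is √(0.27² + 2 × 0.075²) = 0.290 mm, which matches step 1. By simulation:

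- Continuous baseline root-area explains about 3% to 12% of the variance of 12-month raw growth. The SE falls by 1 − √(1 − R²), from 1 − √0.97 = 1.5% to 1 − √0.88 = 6.2%.
- The 10 mm² split explains about 1% to 7%. The SE falls by about 0.6% to 3.5%.

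**5. Error rates on the raw scale.** Trials of 400 patients were simulated with the arms balanced on the 10 mm² split (assumed root-area mean 2.7 mm, SD 0.4 to 0.8 mm, slope-level regression on complete data). Without size, type I error was 0.045 to 0.054. Power was 0.943 to 0.955 without size and 0.950 to 0.957 with it.

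**6. What a chance imbalance would do on the raw scale.** Take assumed typical lesions of 6 and 13 mm² for the two strata. Sham growth is 2.13 and 3.06 mm²/year, a gap of 0.93. The 0.11 mm effect, evaluated at 8 mm², is 0.70 mm²/year. If the arms differed in the share of large lesions by d, the unadjusted difference would shift by 0.93 × d:

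- d = 2 points: 0.02 mm²/year, 3% of the effect
- d = 5 points: 0.05 mm²/year, 7%
- d = 9.5 points: 0.09 mm²/year, 13%

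The last value of d is only an outer illustration (38/400). The documents report no such difference between the arms.

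**The case against.** The strongest defence concerns the primary scale. The square root is chosen to remove the dependence of growth on size, which is an implicit reason for having no size-by-time term. Baseline area is itself a response value in the MMRM, so a size main effect is partly redundant. Protocol 11.7.1 leaves analysis detail to the SAP, and the SAP's sample-size sentence speaks of an analysis of variance rather than specifying the MMRM. Much of this stands, and it is why the effect on the primary result is expected to be nil or small. It does not remove the contradiction with protocol 11.3, which refers to the MMRM itself. Nor does it reach the raw-area analysis, where the rationale does not apply. Because the model has its own treatment intercept, having baseline as a response does not adjust the slope difference for size.

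The SAP also uses 3-level size covariates in the two stratification-error analyses. That partly covers the primary scale, but no size-by-time term is stated there and neither analysis is specified for raw area.

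Two stronger readings are tempting. First, a reader might infer from the 38 patients placed in the wrong size stratum that the arms are unbalanced on size. The documents do not show that. The SAP reports that the randomization center inspected the balance on size and was reassured, and a wrong stratum label before assignment does not by itself unbalance the arms. Second, a reader might infer that the Year 2 move to untransformed area rests on this raw-area analysis, since Year 2 SAP 4.2.1.2 says "the mean GA growth (slope) has shown similar results with or without square root transformation". That section does not name the analysis or model it relies on, so the link is unproven.

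**Conclusion.** The point holds as an inconsistency in pre-specification, with a modest statistical consequence. The protocol says the MMRM includes the stratification factors, the SAP says the same of its analysis, and the operative model leaves out one of the three listed. The raw-area analysis inherits the omission on the scale where size matters by the SAP's own reasoning.

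On the square-root scale there is no loss if slope is independent of size, and the 97% power is unaffected. On the raw scale the gain is the small SE reduction in step 4 plus protection against chance imbalance. These raw-scale figures rest on an assumed baseline size distribution and an SD back-calculated from the 0.057 mm.

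A reader might go further and call the raw-area estimate biased or its test invalid. The working does not support that: a chance imbalance in a randomised comparison is not systematic bias, and the simulated type I error stays near 5%.

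**What to change.** Add baseline GA size (below 10 versus at least 10 mm², corrected value rather than the mis-assigned stratum) and size by time to the section 7.2 model, so that it matches protocol 11.3. In the raw-area analysis add size by time, preferably with continuous baseline size, since most of the precision gain comes from there.

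The cost is a few lines of SAP wording and no new data, because the SAP already plans size covariates elsewhere. The downside is that the size main effect is partly redundant with baseline area as a response; the useful term is size by time. The Year 2 SAP records that the Year 1 primary analysis has been conducted. If the model was not changed before then, report the size-adjusted results as labelled supportive analyses and record the reason for the omission, leaving the pre-specified primary result in place.

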- █ [REDACTED]
- █ [REDACTED]
- █ [REDACTED]
- █ [REDACTED]
- █ [REDACTED]

SENSITIVITY ANALYSES

Sensitivity Analyses for Missing Data

For the analyses of the primary outcome, the MMRM analysis does not require data imputation and uses only the observed data. Moreover, assuming that the missing data are MAR, the model yields valid results that are comparable to those obtained by applying MI under the MAR assumption.

Four analyses described by Miller et al. (2001) will be performed for further insight into the potential impact of missing data on the results:

1. the observed means from the active arm and the sham arm will be imputed to patients with missing data in the arm they were allocated to;
2. the average of observed means from the active arm and the sham arm will be imputed to all patients with missing data;
3. the observed mean from the sham arm will be imputed to all patients with missing data.
4. the observed means from the active arm and the sham arm will be imputed to patients with missing data in the opposite arm they were allocated to (a “cross-over” scheme);

These four sensitivity analyses make different assumptions about missing data, and are likely to be increasingly biased against a true treatment effect. A robust treatment effect would be expected to remain statistically significant in analyses 1 to 3, since these are likely to be much less biased than analysis 4 under the assumption of a true treatment effect.

To check the sensitivity of the results of the primary efficacy analysis (using the primary estimator as described in section 7.2) to the MAR assumption, MI based on models compatible with Missing Not At

CONFIDENTIAL

Random (MNAR) missingness mechanisms will be used. Two approaches, using SAS' PROC MI, will be considered:

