4.2.1.3.1. Miller imputation of missing data

For the analyses of the endpoint, the Mixed-Effects Repeated Measures (MMRM) analysis does not require data imputation and uses only the observed data.

Four analyses described by Miller et al. (2001) will be performed for further insight into the potential impact of missing data on the results:

1. the observed means from the active arm and the sham arm will be imputed to patients with missing data in the arm they were allocated to;
2. the average of observed means from the active arm and the sham arm will be imputed to all patients with missing data;
3. the observed mean from the sham arm will be imputed to all patients with missing data.
4. the observed means from the active arm and the sham arm will be imputed to patients with missing data in the opposite arm they were allocated to (a “cross-over” scheme);

These four sensitivity analyses make different assumptions about missing data and are likely to be increasingly biased against a true treatment effect. Therefore, they will be used only for sensitivity purposes.

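### The own-arm mean imputation is not biased against a treatment effect as the Year 1 SAP says, and its test is too lenient; if growth is imputed, passing analyses 1 to 3 adds almost nothing to the complete-case result

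*SAP*

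**What the plan says.** Year 1 SAP, Sensitivity Analyses for Missing Data, lists four analyses. In the first, "the observed means from the active arm and the sham arm will be imputed to patients with missing data in the arm" of their own allocation. In the second, everyone with missing data gets the average of the two arm means. In the third, everyone gets the Sham mean. In the fourth, patients get the opposite arm's mean. Of all four the SAP says that they "are likely to be increasingly biased against a true treatment effect". It then sets a benchmark: "A robust treatment effect would be expected to remain statistically significant in analyses 1 to 3".

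The section does not say whether a visit level, a change or a slope is imputed, nor how the standard error is computed afterwards. Two other places point to visit levels: the primary model's response is the square root of GA area at each visit, and Year 2 SAP 4.2.1.3.2 describes the Miller method as filling one value per missed visit.

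Year 2 SAP 4.2.1.3.1 repeats the four analyses and the bias statement ("These four sensitivity analyses make different assumptions about missing data and are likely to be increasingly biased against a true treatment effect") but not the benchmark.

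**The concern.** Giving every missing patient the mean of their own arm cannot pull the arms together. It leaves the difference where it was and adds constants to the sample, which makes an ordinary standard error too small. An analysis described as leaning against the drug would then lean slightly towards it, and it is one of the three whose significance is to be read as robustness.

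The unstated imputed quantity matters as well. If a visit mean of square-root area is filled in, a patient with a large baseline lesion can be given a Month 12 value well below it. That noise can cost a true effect its significance for reasons unrelated to the missing-data scenario being tested. One reading makes the benchmark nearly empty; the other can make it fail a real effect.

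**Working it through.** **Inputs from the documents.** About 400 patients, 1:1, so n = 200 per arm. Error rate: "The overall (one-sided) false positive error rate in this trial is 0.025". Effect: 0.11 mm. Smallest significant estimate: 0.057 mm. Stated power: 97%. The alpha deduction per DSMB meeting is not applied, because the number of meetings is not given.

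**Assumptions.** Month 12 values are missing completely at random, in a fraction m of 5% to 20%, equal in both arms unless stated. Imputed values are analysed as if observed. The SD of baseline square-root area is b = 0.7 mm, with a range of 0.4 to 1.0. Growth is independent of baseline. The test is a two-sample comparison of 12-month growth, standing in for the slope contrast.

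**1. The plan's own figure.** SE = 0.057/1.96 = 0.0291, so s = 0.0291/√(2/200) = 0.291 mm. Power = Φ(0.11/0.0291 − 1.96) = Φ(1.82) = 96.6%, against 97% stated. At two-sided 0.01 it is 88.6%, against the SAP's nearly 90%.

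**2. If growth is imputed.** Let D be the complete-case difference. The estimate becomes f × D, with f = 1 (analysis 1), 1 − m (analyses 2 and 3) and 1 − 2m (analysis 4).

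- Ordinary SE: √(2s²(1−m)/n), because the constants add essentially no spread.
- True SE: f × √(2s²/(n(1−m))).
- Ratio of ordinary to true: (1−m)/f, which is 1 − m, 1, 1 and (1−m)/(1−2m).
- Two-sided size: 2[1 − Φ(1.96 × ratio)].

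For analysis 1 at m = 10%: 1.96 × 0.9 = 1.764, giving 7.8%.

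| m | Analysis 1 | Analyses 2, 3 | Analysis 4 |
|---|---|---|---|
| 5% | 6.3% | 5.0% | 3.9% |
| 10% | 7.8% | 5.0% | 2.7% |
| 15% | 9.6% | 5.0% | 1.7% |
| 20% | 11.7% | 5.0% | 0.9% |

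A t-test simulation (40,000 runs per null case) gave 6.3%, 7.8%, 9.6% and 11.7% for analysis 1. With a true difference of −0.11, its mean estimate was between −0.1095 and −0.1106, so it is not attenuated.

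The z-statistic of analysis 1 is the complete-case z divided by 1 − m. For analyses 2 and 3, (1−m)D/√(2s²(1−m)/n) = D/√(2s²/(n(1−m))), which is the complete-case z itself. With unequal missingness analysis 2 stays at 5.0%. Analysis 3 moves to 3.8% (20% active, 10% Sham missing) or 6.5% (10% active, 20% Sham).

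**3. If visit means of square-root area are imputed.** An imputed patient's change is a group mean minus that patient's own baseline. The average per-patient variance becomes v = (1−m)s² + m·b².

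*Analysis 3.* The difference is (1−m)D minus m times the baseline difference between the two sets of missing patients. Its true variance is (1−m)²·2s²/(n(1−m)) + m²·2b²/(nm) = 2v/n, equal to the ordinary one. Size stays near 5%, but the SE grows.

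- m = 10%: v = 0.9 × 0.0846 + 0.1 × 0.49 = 0.1251; SE = 0.0354; z = 0.099/0.0354 = 2.80; power Φ(0.84) = 80%. Complete-case: SE = √(2 × 0.0846/180) = 0.0307, power 95%.
- m = 20%: v = 0.1657; SE = 0.0407; z = 0.088/0.0407 = 2.16; power Φ(0.20) = 58%. Complete-case: 92%.
- Simulation gave about 94% falling to 78%, and 92% falling to 57%.
- At m = 10%, b from 0.4 to 1.0 gives 90% down to 66% by formula (90% to 64% simulated).

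*Analysis 1.* The squared ratio is (1−m)v/(s² + m·b²). At 10% this is 0.9 × 0.1251/0.1336 = 0.843, size 7.2%. At 20% it is 0.8 × 0.1657/0.1826 = 0.726, size 9.5%. A three-visit linear model with unstructured covariance gave 5.7% to 6.2% at 10% and 8.4% to 9.8% at 20%, for baseline SDs of 1.0 and 0.6.

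**The case against.** Several stronger readings are tempting and do not hold.

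- *A reader might infer that all four analyses have wrong standard errors.* With growth imputed and equal missingness, analyses 2 and 3 have correct size and analysis 4 is conservative. Only analysis 1 is clearly too lenient.
- *A reader might infer that the SAP's robustness benchmark has a false-positive rate of up to 12%.* The benchmark requires analyses 1, 2 and 3 together. Simulated under the null, that joint rule rejected in about 4% to 5% of trials (4.2% to 5.6% across settings, under both readings). The inflation belongs to one component that never decides alone.
- *A reader might infer that analysis 1 always passes.* That follows only if growth is imputed. With visit means and b = 0.7 mm, it stayed significant in 89% (10% missing) and 78% (20% missing) of trials whose complete-case test was significant.
- *A reader might say that imputed shrinking lesions contradict the protocol.* Protocol 4.1 calls the loss of vision irreversible; it does not say this of lesion area on FAF.

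The SAP's sentence can also be read as ranking the four analyses, and the ranking is sound for the estimates: the factors are 1, 1 − m, 1 − m and 1 − 2m. Analyses 2 and 3 tie, however, and analysis 1 is not biased against an effect at all.

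The variance method is not shown, so the ordinary SE is an inference from silence. That stands as a condition on every error rate above. The SAP also limits these techniques to sensitivity use and separately plans multiple-imputation shift and pattern-mixture analyses. This reduces the consequence, but it neither corrects these four p-values nor withdraws the benchmark.

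**Conclusion.** The point holds for analysis 1 and for the meaning of the benchmark, not for all four analyses.

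If growth is imputed with an ordinary standard error, analysis 1 has an unattenuated estimate and a two-sided size of about 6% to 12% over the assumed 5% to 20% missing. With equal missingness, significance in analyses 1 to 3 is then practically the complete-case result restated. If visit means are imputed, as the text elsewhere suggests, the size of analysis 1 lies between about 5% and 10%. The larger problem is then lost power in analysis 3, whose extent depends heavily on a baseline SD that the documents do not give.

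The primary MMRM and its p-value are untouched. In Year 2 only the bias statement carries over. This is worth correcting before the analyses are used as evidence of robustness, but it does not threaten the primary conclusion.

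**What to change.** In the Year 1 SAP, keep the four scenarios (own arm, average, Sham, cross-over) but run each as multiple imputation with PROC MI, which is already specified. Condition on the patient's baseline and observed visits, apply the scenario to mean growth, and combine the results by Rubin's rules. This settles both the imputed quantity and the variance method. Delete the statement that analysis 1 is biased against a true effect. Make the same changes in Year 2 SAP 4.2.1.3.1.

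The cost is SAP wording and modest programming. No data collection, sample size or primary analysis changes.
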